#### 9.2.1.1 Crossover Phase: Supportive Analyses of the Primary Efficacy Analysis

A secondary (supportive) descriptive summary of the primary efficacy measure will be provided using the per-protocol population, according to randomized treatment group for each dose.

#### 9.2.1.2 Crossover Phase: Subgroup Analyses

Subgroup summaries comparing MS1819 to porcine PERT will be provided for:

- CFA level while receiving porcine PERT (<80%, ≥80%)

- Gastric acid suppression use (yes, no)

The descriptive summary will be repeated for each subgroup for each dose using the mITT population, according to randomized treatment group.

## 9.2.2 Crossover Phase: Secondary Efficacy Analyses

All secondary efficacy analyses will be presented separately for each dose of the crossover phase.

### 9.2.2.1 Coefficient of Nitrogen Absorption

CNA at the end of each treatment period (Visit 6, Visit 9) will be analyzed. CNA will be expressed as the percentage of nitrogen (protein) absorbed from the subject's diet.

CNA will be calculated using 2 data points:

- Nitrogen consumption in grams/24h (converted from fat consumption in grams/72h as provided by the qualified dietician at each site)
- Nitrogen excretion in grams/24h as provided by the central laboratory

CNA will be calculated as follows:

$$\frac{(\text{Grams/24h of nitrogen consumed} - \text{Grams/24h of nitrogen excreted}) \times 100}{\text{Grams/24h of nitrogen consumed}}$$

CNA at the end of the first period (Visit 6) and CNA at the end of the second period (Visit 9) will be summarized by treatment group for each dose using descriptive statistics. For the summary of CNA, if a subject switches study treatments (i.e. MS1819 to PERT or PERT to MS1819) during the confinement period, prior to the end of the stool collection, then the CNA value during that confinement period will be excluded from the summary. Missing CNA values will not be imputed.

A secondary (supportive) descriptive summary of CNA will be provided using the per-protocol population, according to randomized treatment group.

Nitrogen consumed (g/24h), nitrogen excreted (g/24h), and CNA (%) will be listed by visit for all subjects in the mITT population.

### 9.2.2.2 Stool Weight

Stool weight during the 72-hour marker-to-marker stool collections will be evaluated at the end of each treatment period (Visit 6, Visit 9). All collected stool will be shipped to the central lab for determination of the stool weight as described under the primary efficacy measure.

Stool weight at the end of each treatment period will be analyzed from stool samples collected during the 2 confinement periods (Visit 6 and Visit 9).

Stool weight at the end of each treatment period (Visit 6, Visit 9) will be summarized by treatment group using descriptive statistics. If a subject switches study treatments (i.e. MS1819 to PERT or PERT to MS1819) during the confinement period, prior to the end

of the stool collection, then the stool weight value during that confinement period will be excluded from the summary.

If a subject has more than one stool weight record for a given visit (Visit 6 or Visit 9) and the correct value is unknown, only the heaviest value will be included in the summary.

Stool weight will be listed by visit for all subjects in the mITT population.

### **9.2.2.3 Malabsorption Signs and Symptoms**

Signs and symptoms of malabsorption will be evaluated at Visits 3, 4, 5, 6, 7, 8, 9, and 10.

The EPI malabsorption symptoms will be evaluated according to the following measures:

- Stool frequency (number of bowel movements per day);
- Stool consistency (graded as 0 = hard, 1 = formed/normal, 2 = soft, 3 = watery, or 4 = overt diarrhea);
- Bloating (graded as 0 = none, 1 = mild, 2 = moderate, or 3 = severe);
- Abdominal pain (graded as 0 = none, 1 = mild, 2 = moderate, or 3 = severe);
- Flatulence (graded as 0 = none, 1 = mild, 2 = moderate, or 3 = severe);
- Incidences of visible oil/grease in stool (Yes/No).
- Increased stool quantity (graded as 0 = none, 1 = mild, 2 = moderate, or 3 = severe); and
- Worsening of overall bowel habit (graded as 0 = none, 1 = mild, 2 = moderate, or 3 = severe).

Stool frequency will be summarized by treatment group for the mITT population using descriptive statistics. Stool frequency will be summarized at Visit 3 (At Randomization), At First Dose, 1 Week Post First Dose, 2 Weeks Post First Dose, and 3 Weeks Post First Dose, as described in Section 3.

The number and percentage of subjects within each category for stool consistency, bloating, abdominal pain, flatulence, incidence of visible oil/grease in stool, increased stool quantity, and worsening of overall bowel habit at each study visit and by treatment group will also be provided Visit 3 (At Randomization), At First Dose, 1 Week Post First Dose, 2 Weeks Post First Dose, and 3 Weeks Post First Dose, as described in Section 3. Shifts from Visit 3 will be presented for stool consistency, bloating, abdominal pain, flatulence, increased stool quantity, and worsening of overall bowel habit for the mITT population by treatment group.

Signs and symptoms of malabsorption will be listed for all subjects in the mITT population.

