The mean CFA for the MS1819 group was 56% (range 7% to 92%), and the mean CFA for the PERT group was 86% (range 57% to 97%). This mean CFA of 56% on a dose of 2240 mg/day MS1819 was similar to the mean CFA of 62% in the chronic pancreatitis study at the same dose. The mean coefficient of nitrogen absorption (CNA) for the MS1819 group was 93% and the mean CNA for the PERT group was 97%. Symptoms of exocrine pancreatic insufficiency were more prominent in the MS1819 group.

MS1819 was well-tolerated, with no remarkable adverse events. Three SAEs occurred during the screening period, but none during the trial itself. Each of these SAEs was due to pulmonary exacerbations of cystic fibrosis. Laboratory values were unremarkable during the trial.

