### **8.3.3 Visit 10: End-of-Study /Early Withdrawal Visit (Day 56 ± 2)**

Patients will return to the clinic for their End of Study visit approximately 2 weeks after their last dose of study drug (either MS1819 or the patient's prestudy porcine PERT). In the event that patients do not complete V9, an Early Withdrawal visit will be held approximately 2 weeks after the last dose of study drug. The procedures scheduled for the End-of-Study visit are the same as those that should be conducted for the Early Withdrawal visit. The following procedures will be performed at the End-of-Study/Early Withdrawal Visit:

- Focused physical exam to evaluate gastrointestinal tract, heart, and lungs
  - Record any changes in AEs and concomitant medication
  - Assess and record malabsorption signs and symptoms
-

- Collect a serum sample for circulating anti-LIP2 lipase antibodies and MS1819 concentrations
- Collect blood samples for vitamin determination (A, D, E, and K)
- Perform a urine pregnancy test (urine dip stick), if applicable

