### 9.1 Definitions

#### 9.1.1 Adverse Event

An AE is any untoward medical occurrence experienced by a patient in a clinical investigation; it does not necessarily have a causal relationship with this study drug. An AE can therefore be any unfavorable and unintended sign, symptom, or disease temporally associated with the use of a medicinal product, whether or not considered related to the medicinal product.

Active or worsening of EPI is not considered an AE for the purposes of this study. Worsening of EPI disease should not be recorded as an AE but should be recorded in the appropriate EPI CRF.

Adverse events may also include postdose complications that occur as a result of protocol-mandated procedures (e.g., invasive procedures such as venipuncture, biopsy, etc.). Preexisting events that increase in severity or change in nature during, or as a consequence of, use of a medicinal product in a human clinical study will also be considered AEs. Any preexisting medical condition or diagnosis associated with a clinically significant laboratory abnormality should be documented on the CRF or eCRF. The Investigator should attempt to establish a diagnosis of the event based on signs, symptoms, and other clinical information. In such cases, the unifying diagnosis should be documented as the AE, rather than the individual signs and symptoms (e.g., runny nose, scratch throat, cough, and low grade fever should be recorded as an upper respiratory infection and not each of the individual symptoms).

An AE does NOT include the following:

- Medical or surgical procedures (e.g., surgery, endoscopy, tooth extraction, transfusion); the condition that necessitates the procedure is an AE
- Any preexisting disease or condition or laboratory abnormality present or detected before the start of administration of study medication that does not worsen
- Laboratory abnormalities without clinical manifestations, which do not require medical intervention, or that do not result in termination or delay of study medication

- 
- Situations where an untoward medical occurrence has not occurred (e.g., hospitalization for elective surgery, social, or convenience admissions)
  - Overdose of any study drug or concomitant medication without any signs or symptoms, unless the patient is hospitalized for observation

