  - Worsening and/or flares of EPI disease activity. This should be recorded in the appropriate EPI CRF. However, if disease worsening meets any of the criteria for an SAE, it must be recorded on the SAE form and reported to the Sponsor or designee within 24 hours of becoming aware of the event.

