## 8. SAFETY EVALUATION

### 8.1 Overview of Safety Analysis Methods

Unless otherwise stated, safety analyses will be presented separately for each dose of the crossover phase and each dose of the extension phase. For the crossover phase, all safety analyses will be performed using the safety population and summarized by actual treatment (MS1819 regardless of period vs. PERT regardless of period) allowing direct intrasubject comparison of the tolerability of MS1819 vs. PERT. For the extension phase, all safety analyses will be performed using the safety population and summarized for each dose. Safety measures summarized will include AEs, laboratory data, vital signs, and concomitant medications. Additionally, exposure to study treatment during the study will be displayed.

Safety data will not be imputed, except for partial and missing dates, which will be imputed only for defining treatment-emergent AEs (TEAEs) and concomitant medications. Imputed dates will not be presented in data listings.

TEAEs will be defined as any AEs that occur or are reported to worsen in severity on or after the date of first dose of study treatment in crossover phase period 1. Partial dates will be imputed for the purposes of defining TEAEs as follows:

- For a missing start day where the month and year are present, the start day will be set to the first day of the month, unless 1) the first day of the month is before the date of first dose of study treatment and the month and year are the same as the month and year of the date of first dose of study treatment, and 2) the end date is on or after the date of first dose of study treatment or the end date is completely missing, in which case the start day will be set to the first day of first dose of study treatment.
- For a missing start day and month where the year is present, the start day and month will be set to January 1st, unless 1) January 1st is before the date of first dose of study treatment and the year is the same as the year of the date of first dose of study treatment, and 2) the end date is on or after the date of first dose of study treatment or the end date is completely missing, in which case the start day and month will be set to that of the date of first dose of study treatment.

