### **9.2.3.4 Signs and Symptoms of Malabsorption**

Signs and symptoms of malabsorption will be evaluated at Visits 11, 12, and 13 (4.4 grams/day) and Visits 14, 15, 16 (6.7 grams/day), as well as at Visit 17.

The EPI malabsorption symptoms will be evaluated as described in Section 9.2.2.3.

Stool frequency will be summarized for the mITT population using descriptive statistics.

The number and percentage of subjects within each category for stool consistency, bloating, abdominal pain, flatulence, incidence of visible oil/grease in stool, increased stool quantity, and worsening of overall bowel habit at each study visit will be summarized.

Signs and symptoms of malabsorption will be listed for all subjects in the mITT population.

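### Non-serious EPI worsening is kept out of the AE data and has no event-level table or listing in the SAP text, so the MS1819 versus PERT tolerability comparison omits it

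*SAP*

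**What the plan says.** - **Recording.** Protocol 9.1.1: "Worsening of EPI disease should not be recorded as an AE but should be recorded in the appropriate EPI CRF". The exception is serious worsening: "if disease worsening meets any of the criteria for an SAE, it must be recorded on the SAE form". Neither document defines the EPI CRF or says which fields it holds.
- **Safety analysis.** SAP 8.1: "Safety measures summarized will include AEs, laboratory data, vital signs, and concomitant medications". The same section presents its tables as a within-patient comparison of how well MS1819 and PERT are tolerated. The TEAE tables (SAP 8.3) and the tables of TEAEs leading to discontinuation (SAP 8.4) are built from AEs.
- **Symptom analysis, crossover phase.** SAP 9.2.2.3: "Signs and symptoms of malabsorption will be evaluated at Visits 3, 4, 5, 6, 7, 8, 9, and 10". The tables cover Visit 3, first dose and weeks 1, 2 and 3 after first dose. The listing is restricted: "Signs and symptoms of malabsorption will be listed for all subjects in the mITT population".
- **Symptom analysis, extension phase.** SAP 9.2.3.4 does the same at Visits 11 to 13, 14 to 16 and 17, again in mITT.
- **mITT.** SAP 4.1 requires at least one valid stool collection and CFA after baseline (crossover phase) or in the relevant stage (extension phase).
- **Background.** On the earlier OPTION trial, Protocol 5.6.3 reports: "Symptoms of exocrine pancreatic insufficiency were more prominent in the MS1819 group". It also says that withdrawals during MS1819 were mainly due to increased EPI symptoms.

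**The concern.** Safety and tolerability of both MS1819 doses is a primary objective (Protocol 6.1, SAP 2.1.1). EPI worsening is the tolerability problem that the OPTION summary ties to MS1819, yet that summary also calls MS1819 well tolerated, with unremarkable AEs. An AE table can thus look clean while patients stop treatment because of EPI symptoms.

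Keeping symptoms of the disease under study out of the AE tables is a legitimate choice, provided they are counted elsewhere. The SAP text names no such place for the EPI CRF records. A reader of the safety tables would be comparing MS1819 with PERT without the component on which the two are most likely to differ.

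**Working it through.** The plan gives no figure of its own to reproduce. The check traces where a record of EPI worsening can surface, then asks how much the visit-based grades could recover.

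**1. Where each kind of worsening appears**

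| Kind of EPI worsening | TEAE tables | SAE tables | Symptom outputs | Disposition |
|---|---|---|---|---|
| Meets an SAE criterion | as an SAE | yes (SAP 8.4) | if in mITT and graded | if the patient withdraws |
| Non-serious, patient in mITT | no | no | only through visit grades | if the patient withdraws |
| Non-serious, treated but not in mITT | no | no | no | if the patient withdraws |

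Disposition (SAP 5.1) gives the reason for withdrawal, but the reasons in Protocol 7.3.4 include no category for EPI symptoms or lack of effect, so the cause may not be visible.

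Protocol 7.3.4 also says that withdrawn patients who received study product enter the mITT efficacy analysis. That conflicts with the mITT definition in Protocol 10.3 and SAP 4.1. SAP section 1 gives the SAP precedence, so the third row stands.

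The Early Withdrawal visit does not close the gap: "an Early Withdrawal visit will be held approximately 2 weeks after the last dose of study drug". The crossover symptom tables stop at week 3, so Visit 10 data would appear only in the mITT listing.

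**2. Spacing of the grades**

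Nominal crossover days are 1, 8, 15, 17, 29, 36, 38 and 56, so the gaps are 7, 7, 2, 12, 7, 2 and 18 days. The 12- and 18-day gaps run from the start of a confinement that can last up to 7 days. With the ±2-day windows, Visit 4 to Visit 5 can reach 17 − 6 = 11 days. In the extension phase, E1, E5 and E11 give gaps of 4 and 6 days.

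**3. Chance that a flare falls between grades**

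Take a 21-day treatment period and a flare of L days starting on any of the 22 − L possible days with equal probability (assumption). The miss probability is the number of start days that overlap no observed day, divided by 22 − L. The recall period is not stated, so three readings are shown:

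- A: a grade describes the day of assessment, on days 8, 15 and 17.
- B: as A, but every confinement day from 17 to 21 is observed.
- C: a grade covers the time since the last contact, so days 1 to 17 are covered.

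| Flare length | A | B | C |
|---|---|---|---|
| 1 day | 18/21 = 86% | 14/21 = 67% | 4/21 = 19% |
| 2 days | 14/20 = 70% | 11/20 = 55% | 3/20 = 15% |
| 3 days | 11/19 = 58% | 9/19 = 47% | 2/19 = 11% |
| 5 days | 5/17 = 29% | 5/17 = 29% | 0 |
| 7 days | 1/15 = 7% | 1/15 = 7% | 0 |

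Under C, if the Visit 6 or 9 grade is completed at the end of a confinement reaching day 21, nothing is missed. The same treatment days apply to period 2 only if it starts on day 22 (29 − 21 = 8, 36 − 21 = 15, 38 − 21 = 17). The actual start depends on passage of the second marker, so these days shift.

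**4. Scale from the earlier trial**

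In OPTION, 5 of 41 enrolled patients (12.2%) discontinued during MS1819. At the same rate (assumption), 36 × 5/41 = 4.4 of the 36 planned patients would do so here. This is not the number lost from the symptom outputs. A patient who stops MS1819 in period 2 after a valid PERT collection stays in mITT, and the protocol does not say how many of the five left because of EPI symptoms.

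**The case against.** **What the other side can say**

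- A reader might infer that EPI flares between visits appear in no efficacy or safety output at all. The documents do not support that. Serious flares reach the SAE tables and listings, withdrawals are tabulated by period with a reason, and worsening that persists to the next contact can show in the grades.
- The EPI CRF may be the malabsorption form itself; SAP 9.2.2.3 labels its eight items as EPI symptoms. In that case the data are already tabulated by treatment, and most items are also shown as shifts from Visit 3. The listing sentence does not restrict itself to scheduled visits.
- Table and listing specifications are a separate document (SAP section 1), and a listing of EPI CRF records there cannot be ruled out.
- The 86% figure is the extreme case. It treats a confinement of up to 7 days as a single day. Two items, increased stool quantity and worsening of bowel habit, describe change and so suggest an interval. Under-treatment on a fixed dose is also more likely to be sustained than to last one day, and at 7 days the miss rate is at most 7%.
- EPI symptoms are a prespecified secondary endpoint, so they are not hidden.

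**What stands**

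All of this limits the size of the gap, and the miss rates can be quoted only as a range. It does not supply an event-level comparison, a rule for unscheduled records or any safety-population output. Even if the EPI CRF is the malabsorption form, treated patients outside mITT remain uncovered.

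**Conclusion.** The point holds in a limited form. As written, the SAP text gives no event-level summary or listing of non-serious EPI worsening. Such worsening is visible only indirectly, through mITT symptom grades by visit and through disposition. The SAP 8.1 tolerability comparison therefore omits it, and for treated patients outside mITT neither symptom nor AE outputs show it.

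The size cannot be fixed from the documents. They give no flare rate, no recall period and no definition of the EPI CRF. For a one-day flare, the chance that the grades miss it runs from 86% down to 19% or less across the recall readings; for a week-long flare it is 7% or less. A reader might also infer that the omission makes MS1819 and PERT look more alike by a known amount. The OPTION experience makes that direction plausible, but nothing in the documents quantifies it.

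The conclusion assumes that the separate table and listing specifications do not already contain these records. The change should be made, but it does not threaten the primary CFA analysis.

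**What to change.** Amend SAP 8.1, 9.2.2.3 and 9.2.3.4 as follows.

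1. Define the EPI CRF and state the recall period of the symptom grades.
2. List every EPI CRF worsening record, scheduled or unscheduled, for the safety population.
3. Tabulate the number and percentage of patients with at least one record by treatment received at the time of the record, or at onset if an onset date is collected. Use patients who took that treatment as the denominator, and place the table beside the TEAE table.
4. If the EPI CRF is the malabsorption form, instead produce the symptom listing in the safety population, with a count of patients showing any worsening from Visit 3. For the extension phase, count from the first visit of the stage (Visit 11 or 14).

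The cost is one table and one listing per dose: two doses in the crossover phase and at most two in the extension phase, so at most four of each. The protocol already requires the records to be made, and no visit is added. If the separate specifications already include this listing, a cross-reference in the SAP covers item 2.

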### **5.6.3 AZ-CF2001, A Phase 2, Open-Label, Multicenter, 2x2 Crossover Trial to assess the Safety and Efficacy of MS1819-SD in Patients with Exocrine Pancreatic Insufficiency due to Cystic Fibrosis**

This trial, referred to as the OPTION trial, was the first experience with MS1819 in patients with cystic fibrosis. The trial began in February of 2019, and all patients completed the trial by July 2019. The trial was conducted in 14 sites, with 11 in the U.S. and 3 in Poland. All sites participated in enrollment. The primary objectives of the trial were to ascertain safety of 2240 mg/day dose of MS1819 in patients with cystic fibrosis and to compare the efficacy of MS1819 to commercial PERT in digestion of fat. The study was not powered for inferential statistics. A total of at least 30 patients were planned to complete the study.

Inclusion criteria were cystic fibrosis patients aged 18 or older, who had been clinically well-controlled while on a stable dose of PERT for at least 30 days. The dose of MS1819 employed was 2240 mg/day. This dose, used previously in a Phase 2 study of chronic pancreatitis, was the highest dose used in man prior to the OPTION study. In discussions

with FDA, it was agreed that the safety profile in the prior study in chronic pancreatitis patients was sufficient to allow this as the dose for a first-time study in cystic fibrosis.

Patients were randomized to begin the study in a treatment arm of MS1819, or a treatment arm using the same PERT, and same dose, they had been receiving prior to enrollment. After three weeks on treatment, a CFA was measured, and the patient was crossed over to the opposite treatment. After three more weeks of treatment, a CFA was measured, and the patient was returned to their pre-study PERT. An end of study visit was done two weeks after completing the treatments or upon early withdrawal of patients.

A total of 46 patients were screened, 41 were enrolled and 32 completed the study. Of the 9 withdrawals, one patient discontinued after completing both study treatment periods, three patients discontinued during treatment with PERT and five patients discontinued during treatment with MS1819. The withdrawals of patients who discontinued during treatment with MS1819 were primarily attributed to increased symptoms of exocrine pancreatic insufficiency.

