	SCREENING		INITIAL TREATMENT PERIOD				SECOND TREATMENT PERIOD			END OF STUDY/EARLY TERMINATION
	1 a	2 (T) b	3	4 (T) c	5 (T) c	6 d	7 (T) c	8 (T) c	9 d	10
Visit Number	1 a	2 (T) b	3	4 (T) c	5 (T) c	6 d	7 (T) c	8 (T) c	9 d	10
Study Week	-3		1	1	2	3	4	5	6	8
Study Days	-21		1	8	15	17	29	36	38	56
Visit Window (days)	V1 to V2 interval ≤21 days			±2	±2	+5	±2	±2	+5	±2
Fecal pancreatic elastase k	X									
Diagnostic Test										
Spirometry	X									
Resume Prescribed PERT										
Switch back to prescribed porcine PERT l									X	

A Screening procedures can occur up to 21 days before V1 through the first day of dosing (V3). As some lab assessments require fasting status, site may utilize a pre-screening telephone consent process to obtain agreement in advance for patients to adhere fasting for at least 8 hours. Patients will also be asked to bring a stool sample to the screening visit.

B This first study telephone call will occur once eligibility for the patient is determined. Instructions on the randomization visit will also be communicated and patients will be told to bring in their prestudy porcine PERT with them for V3.

C Visits 4, 5, 7, and 8 are telephone visits to assess any changes to AEs and concomitant medications in addition to confirming the visit date for the next scheduled supervised confinement.

D Visit 6 and Visit 9 are the first and second scheduled confinement visits and can take up to 7 days. A 5-day window is permitted around the scheduled confinement for both V6 and V9 to accommodate for scheduling. Dosing must have occurred for at least 16 days prior to the start of the scheduled confinement.

E The Focused Physical Exam will evaluate gastrointestinal tract, heart, and lungs.

F At the end of V6 (after the last stool sample has been collected), Patients that were randomized to MS1819 (on either the 2240 or 4480 mg/day dose) will begin treatment with their prestudy porcine PERT. Patients that were randomized to their prestudy porcine PERT will begin treatment with MS1819.

G The stool samples will be sent to the central laboratory and CFA, CNA, and stool weight will be measured.

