#### **7.3.4 Removal of Patients from the Study**

A patient may be withdrawn from the study at any time for any of the following reasons:

- Lost to follow-up
- Withdrawal of consent, for any reason, at any time
- Major protocol deviations that could compromise the interpretation of the results
- Occurrence of an immunoallergic reaction
- Occurrence of an adverse reaction (i.e., an SAE related to IMP) that justifies the discontinuation of the IMP
- Pregnancy

The date of withdrawal and the reason for withdrawal must be fully documented in the case report form (CRF) and a short narrative description should be added in the patient's medical records.

If at the time of withdrawal, the patient has received the investigational study product (partially or totally), study staff should encourage the patient to attend the Early Withdrawal Visit for follow-up safety investigations. These patients will be included in the mITT efficacy analysis and safety analysis.

If the reason for discontinuation is an AE, then the Investigator will seek to obtain follow-up information and to document the event until its resolution or stabilization. In any case, the Investigator will take all necessary measures to ensure the patient's safety and ensure the patient is treated in accordance with local standard of care.

If a patient is lost to follow-up, then the Investigator should make every effort to obtain maximum information on the reasons for the nonattendance to the visit and on the patient's state of health. All attempts will be documented in the patient's medical records.

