### 4.1 Modified Intent-to-Treat Population

The modified intent-to-treat (mITT) population for the crossover phase includes all randomized patients receiving at least one dose of treatment and having at least one valid stool collection and CFA post baseline while receiving their assigned study drug..

The mITT population for each stage of the extension phase includes all enrolled patients receiving at least one dose of treatment and having a valid stool collection and CFA during the relevant stage of the extension phase.

A stool sample will be considered valid if the date and time associated with the second blue dye marker is recorded, indicating that the stool sample collection is complete.

The mITT population will be used for efficacy analyses. Subjects will be analyzed according to the treatment group to which they were randomized for the crossover phase, regardless of the actual treatment received, unless stated otherwise.

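### Malabsorption symptoms are tabulated and listed only for patients with a valid CFA, so MS1819-first patients who leave before completing Visit 6 lose their on-treatment symptom grades

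*SAP*

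**What the plan says.** **Population for symptoms.** SAP 9.2.2.3 says: "Stool frequency will be summarized by treatment group for the mITT population using descriptive statistics". Shifts from Visit 3 are also given for the mITT, and the listing is limited in the same way: "Signs and symptoms of malabsorption will be listed for all subjects in the mITT population". The counts by grade name no population, but SAP 4.1 supplies a default: "The mITT population will be used for efficacy analyses". Protocol 10.3 likewise assigns the mITT to all efficacy endpoints, and Protocol 7.2.2 makes symptoms a secondary efficacy endpoint.

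**Entry to the mITT.** SAP 4.1 admits dosed, randomised patients "having at least one valid stool collection and CFA post baseline while receiving their assigned study drug". On validity it adds: "A stool sample will be considered valid if the date and time associated with the second blue dye marker is recorded". Protocol 10.3 sets the same CFA condition.

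**Timing.** Symptoms are assessed at Visits 3 to 10. Visits 4 and 5 are calls at about Days 8 and 15. The first stool collection is at Visit 6 (Day 17, window +5), and a footnote to the Schedule of Assessments adds: "Dosing must have occurred for at least 16 days prior to the start of the scheduled confinement".

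**Withdrawn patients.** Protocol 7.3.4 says of patients who withdraw after receiving product: "These patients will be included in the mITT efficacy analysis and safety analysis".

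**The concern.** The symptom endpoint is restricted to patients who got as far as a completed stool test, and bad symptoms are a likely reason for not getting that far. OPTION shows that this can happen: Protocol 5.6.3 reports five discontinuations during MS1819, "primarily attributed to increased symptoms of exocrine pancreatic insufficiency".

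The safety outputs do not fill the gap. Under Protocol 9.1.1, worsening EPI goes on its own form and becomes a reportable event only if it meets SAE criteria. SAP 8.1 does not include symptoms among the safety measures to be summarised. For an early leaver with non-serious symptoms, the symptom form is the only graded record, and no planned table or listing shows it. At stake is whether the week 1 and week 2 symptom tables describe everyone who took MS1819 or only those who tolerated it long enough to be tested.

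**Working it through.** **1. Earliest possible CFA.** Under Protocol 8.3.3.1 the second dye marker is swallowed on Day 4 of confinement. If confinement starts on study Day 17, that is Day 20, so no valid collection can exist before about Day 20. The calls at Days 8 and 15 come earlier.

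**2. Who loses which records.**

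| Patient who leaves the study | CFA available? | In mITT? | On-treatment symptom records |
|---|---|---|---|
| MS1819-first, before completing Visit 6 | No | No | MS1819 grades from Visits 4 and 5 lost |
| PERT-first, during MS1819 in period 2 | Normally, Visit 6 on PERT | Yes | MS1819 grades from Visits 7 and 8 kept |
| PERT-first, before completing Visit 6 | No | No | PERT grades from Visits 4 and 5 lost |

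Visit 3 is the randomisation and first-dose baseline, so the on-treatment loss is at most two calls per patient, and none if the patient leaves before the Day 8 call. The Early Withdrawal visit (Protocol 8.3.3) records symptoms but collects no stool, so it cannot restore mITT membership. Its record drops out of the listing too, although it is taken about two weeks after the last dose and is not a summary time point.

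**3. Planned numbers.** Protocol 7.3.1 plans about 36 enrolled for 30 completers at 20% withdrawal. 30 × 1.20 = 36 reproduces this. Dividing instead, 30 / 0.80 = 37.5, gives 38, which is close. With 1:1:1:1 allocation (SAP 2.4), 36 / 4 = 9 per sequence and 18 per dose.

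**4. Expected loss from the MS1819 column.** In OPTION, 41 were enrolled and 9 withdrew, 5 of them on MS1819 (5/41 = 12.2%) and 3 on PERT (3/41 = 7.3%). The split by period is not given, so one half in period 1 is assumed.

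- Using OPTION directly: 18 × 5/41 = 2.2 MS1819 withdrawals per dose; × 0.5 = 1.1.
- Using the planned rate: 0.20 × 36 = 7.2 withdrawals; × 5/9 = 4.0 on MS1819, or 2.0 per dose; × 0.5 = 1.0.
- With none or all of them in period 1, the range is 0 to about 2 per dose.
- Chance of at least one loss among 9 MS1819-first patients: 1 − (1 − 5/41)^9 = 69%. At the planned rate, 0.20 × 5/9 = 0.111, it is 65%.

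**5. The same sum for PERT.** 18 × 3/41 = 1.3 per dose; × 0.5 = 0.7. The two columns differ by less than half a patient per dose in number. The likely difference is in kind, since only the MS1819 withdrawals are attributed mainly to EPI symptoms.

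**6. What one loss could do to a table.** As an illustration with assumed counts, take 18 patients exposed to MS1819 at one dose, with 2 severe among those retained. One lost patient, also severe, turns 3/18 = 17% into 2/17 = 12%. Two lost turn 4/18 = 22% into 2/16 = 12.5%. This can arise only at week 1 or 2 and only if the lost patients were severe at that call.

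**7. Extension phase.** SAP 4.1 requires a valid CFA within the relevant stage, and SAP 9.2.3.4 uses that population for the stool-frequency summary and the symptom listing. There is no second period to supply a CFA, so anyone who leaves a stage before its collection loses the symptom record for that stage.

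**The case against.** The strongest reply is that little is hidden. SAP 5.1 tabulates, for all randomised subjects by sequence and dose, who withdrew from each period and why, and adds a disposition listing. That stands. A reader might infer that these patients vanish from the report, and they do not. What disappears is the graded symptom data.

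It can also be said that the rule is even-handed. PERT-first patients who leave in period 1 are dropped in the same way, so a bias towards MS1819 is not guaranteed. That stands as well. OPTION supports a direction but not a certainty, and it used immediate-release capsules at 2240 mg/day, not the enteric capsules of this crossover.

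A reader might take the percentages in step 6 as the size of the bias. The documents do not support that: the severe counts are assumed, and SAP 9.2.2.3 plans no table of worst grade. At week 3 a patient who left before Visit 6 has no record under either population, because SAP 9.1.1 does not replace missing data.

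A reader might also extend the point to weight, BMI and vitamins. Almost nothing would be recovered there. After Visit 3, weight is next taken at Visit 6 and is not taken at Early Withdrawal. Vitamins at Early Withdrawal are drawn about two weeks after the last dose and are not a summary time point.

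Finally, the SAP follows Protocol 10.3, and SAP Section 1 gives the SAP precedence. That settles which mITT definition governs the analysis. It leaves Protocol 7.3.4 in conflict with Protocol 10.3, and it gives no reason for a symptom analysis to depend on a stool test.

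**Conclusion.** The point holds as a limited one. On the plan's own definitions, an MS1819-first patient who leaves before completing Visit 6 loses one or two on-treatment symptom records from every table and listing, and the adverse event data do not recover them unless the event is serious. The same loss falls on PERT-first early leavers, but OPTION's withdrawals suggest that it removes worse symptoms from the MS1819 column, so the MS1819 profile at weeks 1 and 2 may look better than it was.

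The expected size is about 1 MS1819-first patient per dose, range 0 to 2. This assumes that OPTION's rate carries over to enteric capsules at both doses and that about half of MS1819 withdrawals fall in period 1. The endpoint is secondary and descriptive, so no error rate or power is affected. The change is still worth making, because it removes an exclusion that depends on the outcome and uses data already collected.

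**What to change.** - In SAP 9.2.2.3, and for extension symptoms in 9.2.3.4, summarise and list symptoms in the safety population (SAP 4.3) by treatment received, using every on-treatment record.
- Add a summary of the last on-treatment grade per treatment, so that early leavers are represented.
- Keep the mITT for CFA, CNA and stool weight. Leave weight, BMI and vitamins as they are.
- Declare the departure from Protocol 10.3 in SAP Section 11, which now lists only the dropped non-inferiority analyses. Protocol 10.1 allows a change that does not alter a principal feature of the protocol to be described in the SAP and study report without an amendment.
- Reconcile Protocol 7.3.4 with the CFA condition in Protocol 10.3 and SAP 4.1, so that they agree on whether withdrawn patients without a CFA are in the mITT.

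The cost is wording and a population flag, with no new data. The one drawback is that symptom and CFA tables will have slightly different denominators, which a footnote can explain.
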